7.1.3 Time to failure or recurrence

Favourable outcome for each participant will be re-classified according to the likelihood that it was a *Failure or Recurrence (FoR) event* on a five-point Likert scale: Definite, Probable, Possible, Unlikely, and Highly Unlikely⁷.

An event will be considered *Highly Unlikely* to be a FoR event only if there is evidence of durable cure; i.e. the primary outcome classification of favourable which required completion of follow-up with negative cultures. A *Definite* FoR event requires clear bacteriological evidence of failure or recurrence (excluding a proven reinfection with exogenous strain of *M. tuberculosis*), a *Probable* FoR event requires some evidence for failure or recurrence (clinical, bacteriological, or radiological) in the absence of clear bacteriology. The remaining participants will be classified as possible or unlikely based on their data. Time of the FoR event/censoring is the same as defined in the time to unfavourable outcome analysis (see Section 7.1.2). The FoR classification will reviewed by an independent clinician, blinded to treatment.

In the time to FoR analyses, the main groups of interest are those classified as having a Definite or Probable FoR event, with censoring of Possible, Unlikely and Highly Unlikely events at the time of the censoring event which met criteria for Unfavourable or Not Assessable in the primary analysis.

Median time to FoR will be calculated for Regimen B, Regimen C, and Regimen D using the Kaplan-Meier estimator.

A hazard ratio with corresponding two-sided 95% confidence intervals and p-value will be estimated for the comparison of Regimen B with Regimen C, and Regimen B with Regimen D. A Cox Proportional Hazards model will be used, adjusted for randomisation protocol (as defined in Section 1.6) and the stratification factor HIV status with the three categories of: HIV negative; HIV positive with CD4 count ≥350 cells/mm³; and HIV positive with CD4 count <350 cells/mm³.

The equality of survivor functions for time to failure or recurrence for Regimen B and Regimen C, and Regimen B and Regimen D, will each be tested using a Log rank test, stratified by randomisation protocol (as defined in Section 1.6) and the randomisation stratification factor HIV status with the three categories of: HIV negative; HIV positive with CD4 count ≥350 cells/mm³; and HIV positive with CD4 count <350 cells/mm³.

The assumption of proportional hazards between the two comparisons will be tested using the proportional hazards test based on the Schoenfeld residuals after fitting the Cox Proportional Hazards models. In the case where there is adequate evidence that the proportional hazard assumptions are violated at the 5% level (i.e. p<0.05), methods where proportional hazards is not a necessary assumption will be used, such as the Wilcoxon test of equality of survivor functions and restricted mean survival time.

Sensitivity analyses will be conducted i) considering different dichotomies of the 5 point scale and ii) assessing the assumption of independent or non-informative censoring (i.e. that the likelihood of an FoR event at the time of censoring is assumed to be the same as for those in whom no censoring occurred) using inverse probability of censoring weights (IPCW)⁸ and multiple imputation(MI)⁹ respectively.

This failure or recurrence analysis will be repeated in subgroups according to baseline characteristics as described in Section 6.3.

7.1.4 Favourable outcome at Week 132

A patient's outcome will be classified as favourable if their last two sputum culture results are negative, unless they have previously been classified as unfavourable. These two sputum results must be from samples taken at separate visits; the latest must be no more than six weeks before their scheduled last efficacy visit (see Section 7.1).

A patient's outcome at their scheduled last efficacy visit will be classified as unfavourable if:

- They are unfavourable at Week 76
- They start any MDR-TB treatment between their Week 76 and scheduled last efficacy visits
- They die between their Week 76 and scheduled last efficacy visits
- At least one of their last two culture results, from specimens taken on separate occasions, is positive.

A patient who does not have a culture result within the window for their scheduled last efficacy visit, having not otherwise been classified as unfavourable, will be regarded as non-assessable if their last two cultures, from specimens taken on separate occasions, are negative. All other patients who do not have a culture result within the window for their scheduled last efficacy visit and do not meet this definition of non-assessable will be classified as unfavourable.

The secondary non-inferiority outcome at Week 132 for Regimen B compared to Regimen C will be analysed using time to unfavourable outcome, thereby using information on all participants. Data from participants whose scheduled last efficacy visit is before Week 132 will be censored at the time of their last visit, unless they have already become unfavourable. Non-assessable participants will be included in the time to event analysis and censored at the time of their last visit.

The survival curve for each combination of strata (randomised protocol and HIV status) will be calculated using a Cox model adjusting for stratification factors and randomised group. The average survival curve for each randomised group will be estimated as a weighted average of the corresponding stratum-specific survival curves, with weights proportional to the number of individuals in each stratum in the randomised group at baseline. The mean of these differences at week 132 is the point estimate for the difference in overall survival function between Regimen C and Regimen B. A two sided bias-corrected 95% CI for the difference in proportion (Regimen C – Regimen B) will be calculated with bootstrap standard errors. Bootstrap standard errors for the risk difference will be used so that the CI of the risk difference (estimated by the risk difference ± 1.96 se assuming the bootstrap distribution is approximately Normal) is bounded between -1 and 1. The bootstrapping will sample 1000 times and be stratified by stratification factors. The seed for the bootstrap simulations will be stored to enable replication of results.

Non-inferiority will be shown if the upper bound of the 95% confidence interval of the difference in proportion of favourable outcomes at Week 132 between Regimens B and C is less than the 10% margin of non-inferiority; this must be shown in both the mITT and PP populations. If non-inferiority is demonstrated, then superiority of Regimen C compared to Regimen B will be declared if the upper bound of the 95% confidence interval of the difference in proportion of favourable outcomes at Week 132 between Regimens B and C is less than zero. For this analysis, the mITT population will be primary and the PP and mPP populations will be sensitivity analyses.

A sensitivity analysis will estimate the proportion unfavourable at Week 132 on the subset of participants randomised at least 132 weeks on or before 30 November 2021 (see Section 6.1.1). For this analysis, non-assessable participants will be excluded. The mITT population will be primary and the PP and mPP populations will be sensitivity analyses.

The above analyses will be repeated for the following comparisons, restricting the population in each case to include only concurrent controls within sites: Regimen B_{lev} and Regimen C, Regimen B_{mox} and Regimen D and Regimen B, Regimen B and Regimen A, Regimen C and Regimen A, Regimen D and Regimen A. The analysis will also be repeated (in both mITT and PP analysis populations) in subgroups according to HIV status.

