3.1.1 Extension of visit window due to the COVID-19 pandemic

The end dates of the Week 76 window will be extended for any Stage 2 patients whose Week 76 appointment is scheduled to occur during the COVID-19 pandemic and did not occur due to restrictions on movement, unacceptable risk of exposure to COVID-19 in connection with the scheduled visit, or any other reason related to the pandemic. For those patients, the Week 76 sputum samples must be taken in a window beginning six weeks prior to the scheduled visit date and ending within the Week 84 visit window i.e. within 14 weeks of the scheduled Week 76 visit date.

3.2 **Primary efficacy outcome**

The primary efficacy outcome measure is the proportion of patients with a favourable outcome (as defined below) at Week 76.

Only data from events occurring before the end of the Week 76 window will be included in the primary analysis of the primary efficacy outcome.

Culture results obtained using acidified Ogawa (Kudoh medium) will be used in the primary analysis, unless missing, when results from Löwenstein-Jensen (LJ) media will be used.

A positive culture is defined as at least one colony and a negative culture is defined as absence of growth (no colonies).

Favourable

A patient's outcome will be classified as **favourable** if their last two culture results are negative unless they have previously been classified as unfavourable. These two cultures must be taken on separate visits (on different days); the latest of which being within the Week 76 window.

Patients that don't have a culture result within the Week 76 window because they were unable to produce sputum or their sample was contaminated, will be classified as favourable if their last two cultures before the Week 76 window are negative and they have not previously been classified as unfavourable; such patients will be identified separately in tables.

Participants with no sputum sample available at Week 76 due to Covid-19 restrictions who are not otherwise classified as unfavourable will be considered unfavourable. Sensitivity analyses will reclassify these participants as i) non-assessable and excluded from the primary efficacy analysis, and ii) favourable if they meet the definition of favourable above, with the latest of the 2 negative culture results being within the Week 68 window, and unfavourable otherwise.

Unfavourable

A patient's outcome will be classified as **unfavourable** in Stage 2 if:

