7 ANALYSIS OF SECONDARY OUTCOMES

7.1 Efficacy outcomes

Secondary efficacy analyses will be carried out on i) data censored at Week 76, and ii) data from all visits occurring on or before the projected Week 96 visit of the last patient randomised i.e. approximately end of November 2021 (long-term efficacy data). A participant's scheduled last efficacy visit will be their latest scheduled trial visit on or before this date. In addition to the comparisons detailed below, analyses of the long-term efficacy data will include comparisons of Regimen C with Regimen D. Comparisons of Regimen C and Regimen D using data up to Week 76 were carried out at the time of the primary analysis but considered exploratory.

Secondary efficacy outcomes will be analysed on the mITT analysis population with the exception of the analysis of favourable outcome at Week 132 to determine the non-inferiority of Regimen C to Regimen B which will be analysed on the mITT, PP and mPP populations.

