These analyses of time to sputum smear conversion and time to sputum culture conversion will be repeated with the alternative definition as time from randomisation to the first negative culture or smear result respectively (without the need for a second negative culture or smear result to confirm). These analyses will only be carried out on data up to Week 76.

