7.1.2 Time to unfavourable efficacy outcome

Time to unfavourable efficacy outcome is defined as the time from randomisation to the first event that results in the definition of an unfavourable efficacy outcome for that patient (as defined in Section 3.2). Patients that do not culture convert during the treatment and follow-up phases (i.e. fail to have 2 consecutive culture negative results), and have not otherwise been called unfavourable, will be called unfavourable at the date of the last visit when a culture positive result was obtained. Patients classified as favourable or not assessable will be censored in this analysis at the date of collection of sputum that yielded their last negative culture result.

Median time to unfavourable efficacy outcome will be calculated for Regimen B, Regimen C, and Regimen D using the Kaplan-Meier estimator.

A hazard ratio with corresponding two-sided 95% confidence intervals and p-value will be estimated for the comparison of Regimen B with Regimen C, and Regimen B with Regimen D. A Cox Proportional Hazards model will be used, adjusted for randomisation protocol (as defined in Section 1.6) and the stratification factor HIV status with the three categories of: HIV negative; HIV positive with CD4 count ≥350 cells/mm³; and HIV positive with CD4 count <350 cells/mm³.

The equality of survivor functions for time to unfavourable efficacy outcome for Regimen B and Regimen C, and Regimen B and Regimen D, will each be tested using a Log rank test, stratified by randomisation protocol (as defined in Section 1.6) and the randomisation stratification factor HIV status with the three categories of: HIV negative; HIV positive with CD4 count ≥350 cells/mm³; and HIV positive with CD4 count <350 cells/mm³.

The assumption of proportional hazards between the two comparisons will be tested using the proportional hazards test based on the Schoenfeld residuals after fitting the Cox Proportional Hazards models. In the case where there is adequate evidence that the proportional hazard assumptions are violated at the 5% level (i.e. p<0.05), methods where proportional hazards is not a necessary assumption will be used, such as the Wilcoxon test of equality of survivor functions and restricted mean survival time.

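### Time to failure or recurrence is also run on the long-term data, but its definitions refer to the Week 76 outcome, so recurrences after the Week 76 window are handled in a contradictory or undefined way

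*SAP*

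**What the plan says.** SAP 7.1 sets two data cuts. "Secondary efficacy analyses will be carried out on i) data censored at Week 76" gives the first; the second is "data from all visits occurring on or before the projected Week 96 visit of the last patient randomised". For the long-term cut it adds a comparison of Regimen C with Regimen D. Where the SAP wants only the shorter cut it says so: for the alternative conversion definitions under 7.1.1, "These analyses will only be carried out on data up to Week 76". Section 7.1.3 contains no such limit.

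Section 7.1.3 gives one set of rules for both cuts:

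- **Category.** Highly Unlikely applies "only if there is evidence of durable cure", which is then spelled out as "the primary outcome classification of favourable which required completion of follow-up with negative cultures". Definite needs clear bacteriological evidence of failure or recurrence other than proven reinfection. Probable needs some clinical, bacteriological or radiological evidence. Neither has a time limit.
- **Censoring.** Possible, Unlikely and Highly Unlikely cases are censored "at the time of the censoring event which met criteria for Unfavourable or Not Assessable in the primary analysis".
- **Event time.** This is taken from 7.1.2, where the event is the "first event that results in the definition of an unfavourable efficacy outcome for that patient (as defined in Section 3.2"). Favourable and not-assessable patients are censored there at their last negative culture.

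Section 3.2 defines the Week 76 outcome and states: "Only data from events occurring before the end of the Week 76 window will be included in the primary analysis of the primary efficacy outcome". Section 7.1.4 defines the outcome at the scheduled last efficacy visit. It adds MDR-TB treatment starts and deaths after Week 76 and applies the last-two-cultures rule at that visit. Neither 7.1.2 nor 7.1.3 cites it.

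**The concern.** The wording of 7.1.3 does not fit the Stage 2 primary outcome. A favourable Stage 2 primary outcome does not require completed follow-up: it is settled within the Week 76 window, while follow-up runs to Week 132. The main Stage 2 primary analysis also has no not-assessable class; that label appears only in its sensitivity analyses and in 7.1.4. Both features do fit Stage 1, whose primary outcome was at Week 132 and did have such a class (protocol 11.2.1).

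What is at stake is whether the long-term hazard ratios (B with C, B with D, C with D) count recurrences that appear after the Week 76 window, and count them alike in each arm. This matters most for Regimen D: protocol 2.2.1 says it may carry a greater risk of failure or relapse than Regimen B because it is shorter and drops two drugs. Protocol 8.7 also relies on long follow-up to make up for the limited sensitivity of the culture methods.

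**Working it through.** There is no plan figure to reproduce; the check is a comparison of rules. Take three patients who finished allocated treatment, were favourable at Week 76, and then recurred. The literal reading uses the primary-outcome definition of Highly Unlikely. The lenient reading applies the Section 3.2 criteria to all long-term data.

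| Course after the Week 76 window | Literal reading of 7.1.3 | Lenient reading | Under 7.1.4 |
|---|---|---|---|
| 1. Culture positive, with a positive among the last two cultures | Highly Unlikely; censored | Definite; criterion 9 is met, so a date can be derived | Unfavourable |
| 2. Culture positive, retreated, last two cultures negative | Highly Unlikely; censored at the last negative culture, which falls after the recurrence | Definite, but no event time unless criteria 5–7 are met | Unfavourable (treatment start) |
| 3. Retreated on clinical or radiological grounds, no positive culture | Highly Unlikely; censored | Probable, but no event time unless criteria 5–7 are met | Unfavourable (treatment start) |

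**Why cases 2 and 3 lack an event time.** Criterion 3 of Section 3.2 counts restarted treatment only before 76 weeks. Criterion 9 looks only at the last two cultures. Criteria 1, 2 and 4 concern stopping, extending or changing allocated treatment, which these patients have completed.

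**Why capture then differs by arm.** The remaining criteria depend on the drug started:

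- criterion 5 (bedaquiline) applies to Regimens A and B only;
- criterion 6 (a second-line injectable) applies to Regimen C only;
- criterion 7 (a nitroimidazole or linezolid) applies to all regimens.

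So B can be captured by 5 or 7, C by 6 or 7, and D by 7 alone. The same retreatment could count as a dated event in one arm and not in another.

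**The censoring rule.** A patient favourable in the primary analysis has no event meeting the unfavourable or not-assessable criteria in that analysis. The 7.1.3 censoring rule therefore gives no date, and only the last-negative-culture rule in 7.1.2 remains.

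**Scale, in follow-up time.** The Week 76 window ends on study day 574 (SAP 5.3): (574 − 1)/7 = 81.9, about Week 82. It ends later for patients with a COVID-19 extension. Protocol 1.1.6 says about 75% of Regimens B and C have efficacy outcomes at Week 132 and the rest are censored between Weeks 96 and 132. Let m be the mean censoring week of that 25% (assumed range 96 to 132; early losses and deaths ignored). Mean follow-up = 0.75 × 132 + 0.25 × m.

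| m | Mean follow-up (weeks) | After Week 82 | Share of all follow-up | Share of follow-up after Week 40 |
|---|---|---|---|---|
| 96 | 123.0 | 41.0 | 33% | 41/83 = 49% |
| 114 | 127.5 | 45.5 | 36% | 45.5/87.5 = 52% |
| 132 | 132.0 | 50.0 | 38% | 50/92 = 54% |

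The protocol's 3% reduction in person-years gives 132 × 0.97 = 128.0 weeks, of which 46.0 fall after the window, within this range. These are shares of follow-up time, not of events.

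**The case against.** The strongest reply is that this is a missing cross-reference which a sensible analyst would resolve correctly.

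- The words "only if there is evidence of durable cure" state a necessary condition, and a patient with a later positive culture does not meet it. Definite has no time limit, and an independent clinician blinded to treatment reviews the classification. This stands: the SAP does not say that late recurrences are Highly Unlikely, and a reader who infers that goes beyond the text. What remains is that the SAP equates durable cure with the primary outcome, so two of its own rules give opposite answers.
- The Week 76 limit in Section 3.2 is worded for the primary analysis only, and criterion 9 has no week limit of its own. This also stands, and it settles case 1. It does not settle cases 2 and 3.
- The mention of not-assessable patients matches 7.1.4 and suggests that the long-term classification was meant. That is plausible, but 7.1.3 attaches the label to the primary analysis.
- Late relapse is captured elsewhere: 7.1.4 counts any MDR-TB treatment start after Week 76, 8.2 has a category for relapse after treatment success, and 8.3 classifies culture status at Week 132. This largely answers any inference that the trial could not show late relapse on Regimen D. These analyses are not full substitutes. Section 7.1.4 mixes recurrence with deaths and other unfavourable outcomes, 8.2 is unadjusted, and 8.3 ignores intermediate cultures, so it would call case 2 cured if the last culture falls in the Week 132 window.

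The sensitivity analyses in 7.1.3 do not close the gap. Inverse-probability weighting and multiple imputation address dependent censoring, not a recurrence coded as cure or left without a date.

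**Conclusion.** The point holds as a conflict and a gap in the long-term run of one secondary outcome. The Week 76 run is not affected, and no primary or non-inferiority conclusion rests on this analysis. On one literal reading a culture-confirmed recurrence after the window is censored. On the lenient reading some late recurrences still have no event time, and whether they are captured depends on the salvage drug and the arm.

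The number of affected patients cannot be derived from the documents and is probably small. With few late events, however, the handling of several could move a hazard ratio. A reader might subtract the 78.8% favourable at Week 132 in Stage 1 Regimen B from the 80% assumed at Week 76 and take the 1.2 points as a late recurrence rate. The documents do not support that: 80% is a planning value based on preliminary results, 78.8% is a final estimate under Stage 1 rules that exclude some patients as not assessable, and the difference includes deaths. Nor should capturing late recurrence be called the main purpose of the extended follow-up; protocol 1.1.6 gives that as safety.

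**What to change.** In SAP 7.1.2 and 7.1.3, state the governing definition for each data cut:

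- **Week 76 cut:** classification, event time and censoring follow Section 3.2.
- **Long-term cut:** they follow 7.1.4 at the scheduled last efficacy visit. Highly Unlikely means favourable at that visit. A Definite or Probable event after Week 76 is timed at the earlier of the first post-Week 76 positive culture that forms part of the recurrence and the first MDR-TB treatment start.

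In 7.1.3, replace the references to the primary outcome and primary analysis accordingly. This concerns analysis definitions only and leaves patient management unchanged.

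The cost is SAP wording plus blinded review of the few patients whose status changes after Week 76, using the review that 7.1.3 already provides for. No new data are needed.

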1.6 Randomisation procedure

Patients were initially randomised to Regimen A, Regimen B, Regimen C, or Regimen D, in a ratio 1:2:2:2, respectively. From protocol version 6.3 onwards randomisation to Regimen A and/or Regimen D were restricted or stopped (Table 1).

Randomisation will be stratified by (1) site, (2) HIV status (split into three strata: HIV negative, HIV positive with CD4 count \geq 350 cells/mm³, and HIV positive with CD4 count < 350 cells/mm³).

Table 1: Randomisation according to protocol version

Protocol version	Allocation ratio	Regimens
6.2	1:2:2:2	A:B:C:D
6.3 or 7.0	1:1:1	B:C:D in countries where the local NTP adopted or has imminent plans to adopt the WHO 2016 short regimen; as for v6.0 elsewhere
8.0 onwards	1:1	B:C

All analyses will be stratified by randomisation protocol to ensure comparisons are made to concurrent controls:

- comparisons of Regimen C to Regimen B will include all participants allocated to these regimens but be stratified by a 3 level variable: v6.2 vs v6.3/7.0 vs 8.0/10.0
- comparisons of Regimen D to Regimen B will be restricted to participants randomised under protocol v6.2/6.3/7.0 and be stratified by a 2 level variable : v6.2 vs v6.3/7.0
- comparisons to Regimen A will be restricted to participants randomised under v6.2 of the protocol

Analyses of the primary endpoint will also be stratified by HIV status as defined above, unless there is insufficient data within strata. If this is the case initially the two HIV positive groups will be combined, but if there is still insufficient data within strata then stratification by randomisation protocol will be prioritised.

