6.1.1 Modelling technique used in analysis

For the primary efficacy analysis the difference in proportions of favourable outcome between Regimen B (B_{mox} and B_{lev} combined) and Regimen C with corresponding 95% confidence intervals and p-values will be estimated using a stratified analysis of the risk difference from each stratum using Cochran-Mantel-Haenszel weights.⁵ The analysis will be stratified by randomisation protocol and HIV status (as defined in Section 1.6).

6.1.2 Non-inferiority of Regimen C compared to Regimen B at Week 76

Non-inferiority will be shown if the upper bound of the 95% confidence interval of the difference in proportion of favourable outcomes at Week 76 between Regimens B and C is less than the 10% margin of non-inferiority; this must be shown in both the mITT and PP populations. An sensitivity analysis will be undertaken using the mPP population.

6.1.3 Superiority of Regimen C compared to Regimen B at Week 76

If non-inferiority is demonstrated, then superiority of Regimen C compared to Regimen B will be declared if the upper bound of the 95% confidence interval of the difference in proportion of favourable outcomes at Week 76 between Regimens B and C is less than zero,. For this analysis, the mITT population will be primary and the PP and mPP populations will be sensitivity analyses.

Secondary analyses will repeat the primary analysis but compare Regimen B_{lev} and Regimen C, Regimen B_{mox} and Regimen C, and Regimen B and Regimen D, restricting the population in each case to include only concurrent controls within site. For this analysis, the mITT population will be primary and the PP population will be sensitivity analyses. Comparisons of Regimen C and Regimen D were carried out at the time of the primary analysis but considered exploratory.

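### Read literally, the Week 132 estimator in SAP 7.1.4 averages each arm's curve over that arm's own stratum mix, so stratum imbalance enters the secondary non-inferiority difference

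*SAP*

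**What the plan says.** SAP 7.1.4 (Favourable outcome at Week 132) analyses the secondary outcome as time to unfavourable outcome. Curves for each combination of randomisation protocol and HIV stratum are "calculated using a Cox model adjusting for stratification factors and randomised group". These are then combined into a single curve per arm, "with weights proportional to the number of individuals in each stratum in the randomised group at baseline". The following sentence reads "The mean of these differences at week 132 is the point estimate", although no differences have been defined up to that point. On the interval, the SAP says "The bootstrapping will sample 1000 times and be stratified by stratification factors"; it does not say whether resampling is also within arm or whether the weights are recomputed. Non-inferiority holds if the upper confidence bound "is less than the 10% margin of non-inferiority; this must be shown in both the mITT and PP populations". The superiority test at Week 132 uses the same estimate.

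The Week 76 primary analysis (SAP 6.1.1) is a "stratified analysis of the risk difference from each stratum using Cochran-Mantel-Haenszel weights", which gives each stratum a single weight applied to the difference within that stratum. The Week 132 sensitivity analysis in SAP 7.1.4 refers back to 6.1.1, but it covers only participants randomised early enough for full efficacy follow-up and leaves out non-assessable participants.

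**The concern.** A stratum-adjusted difference should compare the two arms over the same population. If Regimen B's curve is averaged over B's strata and Regimen C's over C's, the two averages describe different populations. They can differ even when treatment has no effect in any stratum. Fitting stratum terms in the Cox model does not prevent this, because the averaging step puts the imbalance back.

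The two adjacent sentences also point to different estimators. Own-arm weights produce one curve per arm and a single difference. A mean of differences suggests stratum-level differences averaged over one common mix. Two programmers could follow the text and obtain different estimates.

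At stake is the estimate that decides non-inferiority and superiority at Week 132. Non-inferiority must also hold in the per protocol population, whose exclusions depend on treatment adherence after randomisation, so stratified randomisation does not guarantee balance there. SAP 7.1.4 repeats the analysis for comparisons involving Regimens A and D, which Protocol 11.4.3 expects to have no more than 50 and about 100 patients. Stratum mixes are likely to vary more in groups of that size.

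**Working it through.** **The plan's own figure.** The documents state no precision for the Week 132 estimator. The nearest figure is 172 evaluable patients per arm at Week 76 (SAP 2.1: 80% vs 82% favourable, 10-point margin, one-sided 2.5%, 80% power). A Farrington-Manning calculation gives exactly 172; the simpler unpooled-variance formula gives 168. Then 172 / (1 − 0.14) = 200 per arm, or 400 in total, as stated. The matching standard error of the difference is √[(0.80 × 0.20 + 0.82 × 0.18) / 172] = √(0.3076 / 172) = 0.0423, or 4.2 points.

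**Algebra.** Let w_B and w_C be the stratum shares in each arm and S_B and S_C the Week 132 survival (favourable) probabilities by stratum.

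- Own-arm difference: Σ w_C S_C − Σ w_B S_B.
- This equals Σ w (S_C − S_B) + Σ (w_C − w_B) S, where w is the average of the two arms' shares (the pooled mix when the arms are equal in size) and S is the average of the two arms' survival in the stratum.
- With no treatment effect in any stratum, the first term is zero. The second is zero only if the mixes match or all strata have the same prognosis.
- With common weights the second term is exactly zero.

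**Illustrations with no treatment effect.** The documents give neither the HIV mix nor risks by HIV stratum, so these values are assumed. Strata are HIV-negative, HIV-positive with higher CD4, and HIV-positive with low CD4. Shares are B (0.76, 0.12, 0.12) and C (0.72, 0.12, 0.16).

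- S = (0.83, 0.78, 0.65): −0.04 × 0.83 + 0.04 × 0.65 = −0.72 points.
- S = (0.85, 0.75, 0.55): −0.04 × 0.85 + 0.04 × 0.55 = −1.20 points.

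Here C looks worse because it has more low-CD4 patients. The reverse imbalance would flatter C by the same amount.

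**Check with fitted Cox models.** Inputs: 200 per arm, no treatment effect, 25% censored between Weeks 96 and 132 (Protocol 1.1.6 says about 75% have Week 132 outcomes), assumed favourable 82% if HIV-negative and 67% if HIV-positive.

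| HIV-positive, B vs C | Algebra | Simulated own-arm minus common-weight |
|---|---|---|
| 20% vs 20% | 0.00 | 0.00 |
| 17.5% vs 22.5% | −0.05 × 0.15 = −0.75 | −0.77 |
| 16% vs 24% | −0.08 × 0.15 = −1.20 | −1.22 |

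**Likely size under stratified randomisation.** "Randomisation will be stratified by (1) site, (2) HIV status" (SAP 1.6), and B and C are allocated equally in every row of SAP Table 1. Simulated site-by-HIV blocks with 400 patients, an assumed 13 sites, an HIV mix of 75/12/13%, the two risk sets above and 6 to 14% random exclusions give:

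- a standard deviation of the spurious shift of about 0.3 to 0.6 points;
- a 95th percentile of about 0.6 to 1.2 points.

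A wider grid (15 to 30% HIV-positive, a prognostic gap of 5 to 20 points, 0 to 14% exclusions) gives a standard deviation of about 0.15 to 0.7 points and a 97.5th percentile of absolute size of about 0.3 to 1.5 points.

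**Against the noise.** If the shift is independent of the remaining error, √(4.2² + 0.6²) = 4.24, an increase of about 1%. Direct simulation agrees: the total standard deviation changes by about 1.5% or less.

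**The case against.** The strongest reply is that the text does not settle on own-arm weights. The sentence on averaged differences fits a common-weight reading, and that may be what was meant. This stands, and it is why the point applies to the literal text. It does not remove the need to correct it, since the sentences disagree and no common weights are stated.

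A reader might infer that the Week 132 result is biased, or that false non-inferiority becomes more likely. The documents do not support either. Allocation is balanced by design, so the shift averages to zero over randomisation. In a binary-outcome approximation with C truly 10 points worse, own-arm weights gave false non-inferiority in 2.0 to 2.8% of trials and pooled weights in 2.6 to 3.1%, so there was no inflation. If the bootstrap resamples within strata but not within arm, its standard error also carries some of this variation. One caveat remains: the simulations used random exclusions. Per protocol exclusions that differ by arm within strata need not average to zero, and the documents give no figures on that.

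A reader might also infer that stratum adjustment is lost altogether. It is not. Late-randomised patients are censored early, so censoring is tied to protocol version, and the Cox model still conditions on protocol version and HIV status in handling it. Only the correction for imbalance is lost.

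Finally, if the baseline weights refer to all randomised patients, exclusions do not alter them, and the standard deviation falls to about 0.3 to 0.5 points. The SAP does not say which is meant.

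**Conclusion.** The point holds as a specification fault in a secondary analysis. On a literal reading, imbalance in HIV or protocol strata shifts the Week 132 difference by Σ (w_C − w_B) S. That conflicts with the following sentence of 7.1.4 and with the Week 76 method. The shift is typically a few tenths of a point and seldom more than about 1.2 points, roughly 0.3 of a standard error (1.2 / 4.2), against a 10-point margin. It could change the conclusion only for a result close to the boundary.

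The algebra needs no assumptions. The sizes rest on an assumed HIV mix, stratum risks and number of sites, and no size was computed for the protocol strata. The Week 76 primary analysis is not affected, and the Week 132 sensitivity analysis that refers to 6.1.1 is a partial cross-check with common weights.

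**What to change.** In SAP 7.1.4:

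- State one set of stratum weights for both arms: the pooled baseline stratum counts of the two regimens being compared, in the analysis population concerned.
- Define the point estimate as the weighted mean of the stratum-specific C minus B differences at Week 132. The sentence on averaged differences then has a clear referent.
- Apply the same weighting rule in each bootstrap sample, and say whether resampling is within arm as well as within strata.
- Use the same rule for the repeated pairwise comparisons.

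This removes the imbalance term exactly, brings Week 132 into line with Week 76, and needs no new data. The edit is a sentence or two and a small change in code. The small downside is timing: SAP v6.0 is dated September 2022, and SAP 7.1 refers to comparisons already carried out at the time of the primary analysis. The change should therefore be logged as a dated, justified clarification that records which weights the existing programs use. If they already use common weights, only the text changes.
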